13.6 SAFETY ANALYSIS

All AEs occurring in the trial will be recorded and compared across the two groups. Comparison of prevalence of SEs between study groups will be expressed as a percentage.

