10.3 STUDY ASSESSMENTS AND PROCEDURES

Patients likely to fulfill the inclusion criteria and not meet any exclusion criteria will be provided with information on the study and invited to attend a subsequent screening visit. Only patients who have signed the informed consent form will participate in any study related procedures including blood testing and ECG.

At screening visit (Assessment 1) subjects will have a physical examination and an EDSS score rated. Blood samples will be taken for renal and liver function and a baseline ECG performed. Patients will complete a nine-hole peg test and a JTT. T25FW will be recorded and the patients invited to complete the MSIS-29, MSWS-12, DASH, AMSQ and SF-36 questionnaires. Patients with any abnormalities on ECG, blood tests will not be invited to a baseline visit and considered a screening failure.

Following screening visit subjects fulfilling the inclusion / exclusion criteria will have two baseline visits (Assessments 2 and 3) at the end of week one and end of week two. The 9-HPT, JTT and T25FW will be repeated to allow for training effects. Patients will be randomised to group A or group B and receive study medication or placebo at baseline visit based on their blinded randomisation (Assessment 3).

The first treatment period will be from the start of week 3 until the end of week 10. Patients will have an assessment at the end of week 6 (Assessment 4) and the end of week 10 (Assessment 5). At both assessments patients will have the 9-HPT, JTT, T25FW, MSIs-29, MSWS-12, DASH, AMSQ and SF-36 recorded. Weeks 11 and 12 will be a washout period (no drug/placebo). Assessment 6 will occur at the end of week 12 and will include recording of 9-HPT, JTT, T25FW, MSIs-29, MSWS-12, DASH, AMSQ and SF-36. Any adverse events will be recorded at each visit as will the use of concomitant medications.

The second treatment period will begin at the start of week thirteen with groups A and B switching study drug / placebo in a blinded manner. The second treatment period will continue for a further 8 weeks with two more assessments at week 16 (Assessment 7) and week 20 (Assessment 8). At both of these assessments subjects will complete the 9-HPT, JTT, T25FW, MSIs-29, MSWS-12, DASH, AMSQ and SF-36. At the end of week 20 and EDSS score will be recorded. Any adverse events will be recorded at each visit as will the use of concomitant medications.

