There will be a final washout period (weeks 21 and 22) after which a final visit (assessment 9) will occur and subjects once again completing 9-HPT, JTT, T25FW, MSIs-29, MSWS-12, DASH, AMSQ and SF-36 and having an EDSS score recorded. Once again adverse events will be recorded.

(See Schedule of Events, page 15)

Figure 2: Schedule of events

Assessment	1 Screening Visit	2 Baseline Visit	3 Base - line Visit	4 Rx Phase 1	5 End of Rx Phase 1	6 End Wash- out phase	7 Rx Phase 2	8 End of Rx Phase 2	9 End of 2 week washout
Time (start/end week)	week 1 (start)	week 1 (end)	week 2 (end)	week 6 (end)	week 10 (end)	week 12 (end)	week 16 (end)	week 20 (end)	week 22 (end of trial)
Informed consent	X								
Serum pregnancy test (female subjects)	X								
EDSS	x							X	X
ECG	X								
Receiving Medication	No	No	Start drug	Continu e drug	Stop drug	Start drug	Continu e drug	Stop drug	Wash out
9- HPT	x	x	x	x	x	x	x	x	X
JTT	x	x	x	x	x	x	x	x	X
T25FW	x	x	x	x	x	x	x	x	X
MSIS-29	x		x	x	x	x	x	x	X
MSWS-12	x		x	x	x	x	x	x	X
DASH	x		x	x	x	x	x	x	X
AMSQ	x		x	x	x	x	x	x	x
SF-36	X		X	X	X	X	X	X	X
Adverse event recording				X	X	X	X	X	X
Concomitant medication recording	X		X	X	X	X	X	X	X
Study Drugs dispensed			X			X			

Description of Study Assessments

Medical and Surgical History will be recorded with particular attention on the diagnosis of MS, duration of MS and MS subtype.

Demographics

The date of birth, gender and race will be recorded.

Physical Examination

The complete physical examination will include the evaluation of the neurological system and a recording of the EDSS score and T25FW.

ECG Test

One ECG including a 12-lead examination will be performed at Screening (assessment 1).

Abnormal findings will be noted for clinical significance. The report will be signed by the investigator.

Clinical Laboratory Tests

1. Haematology: haemoglobin, WBC, RBC, platelet count
2. Biochemistry: creatinine or creatinine-clearance, sodium, potassium, liver function tests
3. All laboratory results will be reviewed and the reports signed by the investigator who will record in the CRF whether they are normal, abnormal but not clinically significant, or abnormal and clinically significant.

Pregnancy Tests

Serum pregnancy test and urine pregnancy test in women of childbearing potential will be performed.

Concomitant Medication

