10.3.3 Method of assigning Subjects to treatment groups

Randomisation

Generation of Randomisation Codes

Subjects were randomised to each of two groups, A or B using the program:

<http://www.graphpad.com/quickcalcs/randomize1.cfm>

The randomisation sequence was generated on 07/03/2012.

Table 1. Randomisation Groups

Randomisation Groups	A = Initial treatment with Fampridine followed by placebo. B = Initial treatment with placebo followed by Fampridine.
----------------------	--

Security and Distribution of Randomisation Codes

The randomisation codes will be kept on the Pharmacy Network Drive in St. Vincent's University Hospital. A hardcopy will be kept in the Pharmacy Department in the clinical trial folder.

The investigators and subjects will not have access to the randomisation codes (double blind).

A copy of the randomisation code and individual product codes will also be kept in a sealed envelope, with signature and date across the seal, which may be opened by the Principal Investigator if an emergency code-break is required. This will be stored in a secure location in the Neurology department but can be accessed by the Principle investigator if needed.

Handling

Pharmacy staff will use the information when dispensing clinical trial medication to each subject to ensure the appropriate medication is dispensed (ie placebo or active).

Retention

The study pharmacist will retain the randomisation codes until the database is locked at the end of the trial. Thereafter, the randomisation code will be made known to the investigators.

Code-Break Mechanisms

In the case of emergency, when knowledge of the subject's study treatment assignment is essential for the clinical management of the subject. Any intentional or unintentional breaking of the blind will be recorded and reported to the sponsor as soon as possible.

After database is locked at the end of the trial.

Blinding

Procedure for blinding of Fampridine versus placebo.

1. Capsules look identical.

Fampridine and placebo capsules look identical.

2. Identical packaging

Fampridine and placebo are packaged in identical packaging.

3. Identical labeling

The label instructions will be identical for both. See copy of label below

Figure 3. Study drug label.

FAMPYRA® 10MG TABLETS OR PLACEBO						
Fampridine 10mg tablets or placebo						14 tablets
Take ONE tablet TWICE daily						
To be taken orally. For clinical trial use only.						Keep out of reach of children.

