13.5 EFFICACY ANALYSIS

Primary efficacy endpoint:

An upper limb responder to fampridine will be defined as a patient with both of the two "on treatment" 9-HPT assessments (assessments 4 & 5 or 7 & 8) improving 20% from the average of the baseline assessments (1, 2 & 3).

Secondary efficacy endpoints:

- a) A secondary measure of upper limb responsiveness will be defined as a 20% improvement in from baseline in the average time taken to complete all seven tasks on the JTT “on treatment” (assessments 4 & 5 or 7 & 8) compared with baseline assessments (assessments 1,2 & 3).
- b) A mobility responder to dalfampridine will be defined as a patient with both of the two “on treatment” T25FW assessments (assessments 4 & 5 or 7 & 8) being better than the maximum of any of the four “off treatment” assessments (assessments 1, 2, 3, & 9). Otherwise the patient will be deemed a non-responder.
- c) The responders to the 9-HPT and/or JTT will be compared to the non-responders in relation to their changes in the DASH and AMSQ on treatment and off treatment at the baseline assessment. The change in the DASH and AMSQ in responders at Assessment 5 or 8 (week 10 or 20) will be compared to non-responders at that time-point.

Upper limb response will be examined at the end of treatment phase 1 and repeated at the end of the trial by comparing patients receiving active drug with those receiving placebo to assess any placebo effect and allow assessment of any residual beneficial effect on those who receive fampridine in treatment phase 1 and then switch to placebo in treatment phase 2. Response will again be considered as a 20% improvement in the 9HPT in the active treatment group compared with placebo and a 20% improvement from baseline in the time taken to complete all seven tasks in the JTT. See earlier comment

- d) The responders to the T25FW will be compared to the non-responders in relation to their changes in the MSWS-12 on treatment and off treatment at the baseline assessment. The change in the MSWS-12 in responders at Assessment 5 or 8 (week 10 or 20) will be compared to non-responders at that time-point.

The patients’ scores on the MSIS-29 (physical) and SF-36 will be examined in relation to the objective changes (responder/non-responder) in the 9-HPT, JTT and the T25FW.

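### Section 13.6 compares adverse events between two groups that, as defined, are crossover sequences both taking fampridine; read literally, this largely cancels any excess on the drug

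*Combined protocol and SAP*

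**What the plan says.** Safety of fampridine is a secondary objective (9.2). Section 13.6 is its only planned comparative analysis and has two sentences: "All AEs occurring in the trial will be recorded and compared across the two groups" and "Comparison of prevalence of SEs between study groups will be expressed as a percentage". It does not mention treatment received, period, or treatment at onset.

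The pair of groups is defined in 10.3.3: "Subjects were randomised to each of two groups, A or B using the program", with "A = Initial treatment with Fampridine followed by placebo. B = Initial treatment with placebo followed by Fampridine". Section 10.3 repeats the labels when it describes the second period, with "groups A and B switching study drug / placebo in a blinded manner". Two-week washouts follow each treatment period (weeks 11–12 and 21–22).

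Section 13.5, on upper limb response, uses different language: "comparing patients receiving active drug with those receiving placebo". Section 12.3 requires onset and end dates for every AE.

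**The concern.** In a crossover trial, sequence is not treatment. If the two groups in 13.6 are A and B, the comparison sets fampridine then placebo against placebo then fampridine. Both sides contain the same exposure, so the quantity of interest, AEs on fampridine against AEs on placebo, is mostly subtracted out.

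This is more than a missing detail. Followed as written, the stated comparison answers a different question from the safety objective. The trial has no data safety monitoring board (12.5), so this end-of-trial comparison is where an excess of common, non-serious AEs would be expected to appear.

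**Working it through.** **Inputs.** From the documents: 80 patients, 40 per sequence (13.2); two 8-week periods (10.1); significance level 0.05 (13.7). Section 13.6 contains no figure to reproduce. The documents give no AE, dropout or period-effect rates, so all of those are assumed.

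**Step 1: full follow-up, no period or carry-over effect.** Let pF and pP be the chance of at least one AE in a fampridine or a placebo period, taken as independent, with washouts ignored. Then

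P(any AE) in A = 1 − (1 − pF)(1 − pP) = P(any AE) in B.

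| pP | pF | A | B | A − B | pF − pP |
|---|---|---|---|---|---|
| 10% | 20% | 28.0% | 28.0% | 0 | 10 points |
| 20% | 35% | 48.0% | 48.0% | 0 | 15 points |
| 10% | 30% | 37.0% | 37.0% | 0 | 20 points |
| 40% | 60% | 76.0% | 76.0% | 0 | 20 points |

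The zero does not depend on the rates, nor on independence: correlation between a patient's two periods enters both sequences in the same way.

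**Step 2: dropout or a period effect.** Let a fraction d leave after period 1 for reasons unrelated to AEs, let second-period risks be k times first-period risks, and write m = k(1 − d). Then

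A − B = [1 − (1 − pF)(1 − m·pP)] − [1 − (1 − pP)(1 − m·pF)] = (1 − m)(pF − pP).

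- Dropout only (k = 1): A − B = d(pF − pP). At 20% v 35% and d = 20%, A = 1 − 0.65 × 0.84 = 45.4% and B = 1 − 0.80 × 0.72 = 42.4%, a difference of 3.0 of 15 points. At 10% v 30% it is 2.0 of 20 points for d = 10% and 4.0 for d = 20%.
- Period effect only (d = 0): A − B = (1 − k)(pF − pP). At 20% v 35% with second-period risks halved, this is 0.5 × 15 = 7.5 points. With first-period risks halved instead (10% v 17.5%, k = 2), it is −7.5 points.

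So A − B is the drug excess multiplied by a factor set by dropout and period, not by the drug.

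**Step 3: what a test would see.** Simulation with 4,000 trials per setting, 40 per sequence, independent periods and no dropout. A v B uses chi-square; fampridine v placebo periods uses exact McNemar. Section 13.6 names neither test.

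| pP v pF | A v B significant | By treatment significant |
|---|---|---|
| 10% v 20% | 5.0% | 34% |
| 20% v 40% | 5.6% | 75% |
| 10% v 30% | 5.0% | 85% |
| 15% v 40% | 5.8% | 93% |

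A v B rejects at about the nominal level. With 20% dropout at 10% v 30%, the figures are 6.6% and 76%.

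A second simulation let risk vary between patients (SD 1 on the logit scale) and added washout AEs at the placebo rate. At 20% v 35% it gave 48.8% in A and 48.6% in B; by treatment, the difference was 14.8 points, average 95% CI 2.2 to 27.4.

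**Step 4: washouts and denominators.** Washouts are 4 of the 20 weeks after first dose. At 20% per 8 weeks, the 2-week risk is 1 − 0.80^(1/4) = 5.4%; over 80 × 2 = 160 patient-washouts that is about 8.6 with an AE. If 30% of patients with an AE on fampridine and 10% on placebo withdraw in that period, the second simulation gives −0.2 points for A − B. By treatment it gives 15.3 points among all who started each treatment, but 12.6 if only patients with both periods are kept.

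**The case against.** The strongest reply is that the authors meant fampridine against placebo. The protocol uses the word group loosely: 13.5, just before the safety section, sets a group on active treatment against placebo, and the safety objective concerns fampridine itself. That reading is plausible and may be the intended one. But 13.5 concerns efficacy, and no safety text says AEs are compared by treatment taken.

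A second reply is that A v B need not be blind to the drug. Split by phase, weeks 3–10 form an ordinary parallel comparison that would show an excess. This is correct, but 13.6 refers to all AEs in the trial and states no split. It follows that a reader who infers that the plan *cannot* show an excess goes too far: the cancellation is complete only for the whole-trial comparison under the Step 1 conditions.

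Two other inferences are tempting.

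- A reader might infer that the sign of A − B follows the period effect and not the drug. The Step 2 formula does not support this: with no drug effect A − B is zero whatever k is, and the sign reverses if the drug lowers AE risk. Both effects are needed.
- A reader might infer that a harmful excess would go unseen and be reported as evidence of safety. The documents do not support this either: each AE is assessed for causality and severity (12.2), and 12.4 requires SUSAR reporting and an annual safety report. These do not replace a controlled comparison, but 13.6 is not the only route by which a signal surfaces.

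The undefined abbreviation SEs in 13.6 is a clerical matter, and the lack of a rule for every detail would be a minor point alone.

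**Conclusion.** The point holds. On the protocol's own definition of its two groups, 13.6 compares sequences rather than treatments, and a whole-trial comparison largely cancels an AE excess on fampridine. The expected difference is zero with full follow-up and no period or carry-over effect. Dropout unrelated to AEs lets through only the fraction d of the excess; a period effect lets through 1 − k of it, which may be sizeable and of either sign.

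The algebra is free of assumed rates. The percentages, confidence intervals and rejection rates are illustrations only. Whether the authors intended A v B is not known; the point is that the text as it stands says that and nothing in the safety sections corrects it. The primary endpoint is not affected.

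**What to change.** Replace the comparison in 13.6 with one by treatment:

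- Assign each AE to the treatment being taken at onset: fampridine period or placebo period. Show AEs starting in a washout separately, by preceding treatment.
- For each treatment, give the number and percentage of patients with at least one AE and at least one SAE, among patients who took at least one dose of that treatment.
- Give the fampridine-minus-placebo difference with a 95% CI that accounts for the pairing of periods within patients and keeps patients who have only one period, for example a risk difference with standard errors clustered on patient.

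Replace SEs with the intended term in the same edit.

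The cost is one paragraph, slightly more analysis work, and queries for missing onset dates. Onset and end dates (12.3) and dispensing records (11.4) are already collected. No visit, test or patient is added, and blinding is unaffected because the code is released to investigators after database lock (10.3.3).

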13.7 THE LEVEL OF STATISTICAL SIGNIFICANCE

A significance level of 0.05 will be used for all analyses.

13.8 CRITERIA FOR THE TERMINATION OF THE TRIAL

The trial will be terminated after the last visit of the last participant.

13.9 PROCEDURE FOR ACCOUNTING FOR MISSING, UNUSED AND SPURIOUS DATA

Data will be analysed as is, with the primary analysis being based on complete case data. The amount and nature of missing data, together with demographic and baseline summaries of these cases will be documented.

13.10 PROCEDURE FOR REPORTING ANY DEVIATION(S) FROM THE ORIGINAL STATISTICAL PLAN

Any deviations from the statistical plan, and additional analyses will be documented and noted in the final report.

14.0 DIRECT ACCESS TO SOURCE DATA/DOCUMENTS

Direct access will be granted to authorised representatives from the sponsor, host institution and the regulatory authorities to permit trial-related monitoring, audits and inspections.

15.0 DATA HANDLING AND RECORD KEEPING

Source documents will be kept in the hospital charts of all participants. Data on CRFs and all other hard copies will be locked in filing cabinets in the Department of Neurology, SVUH. Electronic data will be held coded on a password-protected database on the H-Drive of the Department of Neurology, SVUH accessible only to members of the study group. Pharmacy records will be kept in the Pharmacy Department SVUH. Electronic files will be kept on the Pharmacy network drive.

15.1 DATA COLLECTION, SOURCE DOCUMENTS AND CASE REPORT FORMS (CRF):

Source documents for this study will include hospital records and procedure reports and data collection forms. These documents will be used to enter data on the CRFs. All data entered on CRFs must be entered legibly. If an error is made, the error will be crossed through with a single line in such a way that the original entry can still be read. The correct entry will then be clearly inserted, and the alterations will be initialed and dated by the investigator.

Data reported on the CRF that are derived from source documents must be consistent with the source documents or the discrepancies must be explained.

All documents will be stored safely in confidential conditions. On all study-specific documents other than the signed consent, the subject will be referred to by the study subject identification number/code.

15.2 DATA REPORTING

Data will be entered in hospital notes and these will act as source data. In addition a number of CRFs will be generated for each study participant. Summary data coded for each participant will be entered in a database stored in a coded password protected excel datasheet accessible only to the study personnel listed above. A study specific number and / or code in the database will identify subjects. The name of any subject or other identifiable information will not be included in any study data electronic file.

16.0 RETENTION OF ESSENTIAL DOCUMENTS

Essential documents will be retained until at least 2 years after the last approval of a marketing application in an ICH region and until there are no pending or contemplated marketing applications in

an ICH region or at least 2 years have elapsed since the formal discontinuation of clinical development of the investigational product. These documents should be retained for a longer period however if required by the applicable regulatory requirements or by an agreement with the sponsor. The investigator/institution should agree to retain the trial-related essential documents as required by the applicable regulatory requirements and until the sponsor informs the investigator/institution these documents are no longer necessary.

All records and documents will be maintained by the investigator for a period of at least 5 years after FDA/European Medicines Agency (EMA) approval of the medicinal product or at least 5 years have elapsed since the formal discontinuation of clinical development of the investigational medicinal product, whichever is longer.

17.0 QUALITY CONTROL AND QUALITY ASSURANCE PROCEDURES

This study will be conducted in accordance with the current approved protocol, ICH GCP, relevant regulations and standard operating procedures. All study participants hold up-to-date GCP training certification. The internal monitor shall ensure excellent quality of data collection and recording is maintained.

18.0 AUDITS AND INSPECTIONS

This trial may be subject to internal or external auditing or inspections procedure to ensure adherence to GCP. Access to all trial-related documents will be given at that time.

19.0 ETHICS

The investigator will have obtained ethics committee approval for the study protocol, PIL and other required study documents prior to starting the study.

Any changes to the protocol will be submitted to the ethics committee. The principle investigator will ensure that all aspects of institutional review are conducted in accordance with current governmental regulations. Protocol amendments will be subject to the same requirements as the original protocol. A progress report will be submitted to the ethics committee at the study end. At the completion or termination of the study, the investigational site will submit a closeout letter to the ethics committee.

19.1 DECLARATION OF HELSINKI

The sponsor will ensure that this study is conducted in accordance with the ethical principles that have their origins in the Declaration of Helsinki.

19.2 GOOD CLINICAL PRACTICE

This study will be conducted in accordance with Good Clinical Practice (GCP), as defined by the International Conference on Harmonisation (ICH) and in accordance with the ethical principles underlying European Union Directive 2001/20/EC and 2005/28/EC.

